	or corticosteroids in the hip candidate for infiltrative				
	treatment within 4 weeks prior to enrolment				
	 subjects with local or systemic infections of the candidate hip, 				
	osteomyelitis or sepsis;				
	subjects undergoing chronic treatment with corticosteroids or				
	immunosuppressants.				
	• subjects who are drug addicts, alcoholics, suffer from				
	psychiatric disorders or have clinical conditions that may				
	compromise the correct interpretation of PROMs or follow-up;				
	• subjects with coagulopathies, platelet aggregation disorders				
	or those on oral anticoagulants or antiplatelet agents that				
	cannot be discontinued during the study period				
	• pregnant and lactating subjects (female subjects of				
	childbearing age must be tested for pregnancy prior to				
	enrolment)				
	subjects with an allergy to porcine collagen.				
PHASE OF THE STUDY	Fase IV post market				
NUMBER OF CENTRES	1 Experimental Centre.				
DESCRIPTION OF THE	MD-Tissue Collagen Medical Device is an injectable medical device				
MEDICAL DEVICE UNDER	based on porcine collagen type I; the collagen content is $100\mu g/2mL$.				
STUDY					
STUDY DURATION	The total duration of the study will be 10 months. There will be a 4-				
	month subject selection and recruitment period and a 24-week				
	treatment and observation period.				
STUDY DURATION PER	The duration of the study for each subject will be in weeks 24.				
SUBJECT					
L					

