T6 weeks/FU:

At 6 weeks from day 0, the endpoints in the Investigation Plan will be assessed.

Including:

- pain assessment using the NRS scale;
- assessment of the mHHS scale;
- clinical assessment of pain on palpation of the trochanter using the NRS scale;
- clinical assessment of stenia in abduction of the lower limb with the dynamometer;
- assessment of analgesic drug consumption when pain occurs
- through clinical diary;
- evaluation of any Adverse Events.

T10 weeks/FU:

At weeks 10 from day i.e. weeks 8 after the end of the treatment, the assessment of the end points in the Clinical Investigation Plan will be carried out again.

Including:

- pain assessment using the NRS scale;
- assessment of the mHHS scale;
- clinical assessment of pain on palpation of the trochanter using the NRS scale;
- clinical assessment of stenia in abduction of the lower limb with the dynamometer;
- assessment of analgesic drug consumption when pain occurs
- through clinical diary;
- evaluation of any Adverse Events.

T24 weeks/FU:

At 24 weeks from day 0 at the end of the Clinical Investigation, all the endpoints of the Investigation Plan will be assessed.

Including:

- pain assessment using the NRS scale
- assessment of the mHHS scale;
- clinical assessment of pain on palpation of the trochanter using the NRS scale;
- clinical assessment of stenia in abduction of the lower limb with the dynamometer;

- clinical evaluation and recording by MRI of signs of the inflammatory and degenerative state of the peritrochanteric region of the hip affected by GTPS.
- evaluation of analgesic drug consumption when pain occurs
- through clinical diary;
- evaluation of any Adverse Events.

Diagnosis, evaluation of inflammatory and degenerative signs on MRI examination of the hip affected by GTPS and evaluation of pain on palpation of the trochanter will be carried out by [name]. The NRS and mHHS rating scales will be administered to the subject by a Co-Investigator. The evaluation of the lower limb abduction stenia will be carried out by a Co-Investigator, by means of a dynamometer, with which three measurements will be taken (with a recovery of 1 minute between each measurement) from which the average will be derived for a more accurate evaluation. The recording of the data in the clinical diary concerning the intake of celecoxib or paracetamol will be performed by the Co-Investigator.

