4.14 Criteria for effectiveness

4.14.1 End Point Primario

The objective of this study is to evaluate the efficacy of the experimental treatment in terms of reduction of referred pain in the peritrochanteric area, of the hip affected by GTPS.

The primary endpoint will be assessed at 10 weeks and will include:

• Evaluation of the NRS score at time 10 weeks compared to time T0. It can be considered clinically significant if at least 50% of the treated subjects show a reduction of at least 3 points on the NRS scale.

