4.16 Early abandonment of the Clinical Study

I Subjects may leave the Clinical study for the following reasons:

- a. at their own request (even without justification);
- b. at the investigator's discretion;
- c. if they experience an Adverse Event.

The reason for abandonment will be stated in the e-CRF.

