5. STATISTICS

5.1 Dimensione del campione

This is a one-sample study. It is assumed that the proportion of successes (patients who have a reduction of at least 3 points on the NRS scale) in the absence of treatment cannot exceed 25%, (H0) while, in section 4.14.1, a success rate of at least 50% (HA) in treated subjects was assumed to be clinically significant.

Under these assumptions, an exact one-tailed binomial test applied to a sample of 49 subjects achieves a power of 95.7% in discriminating the 25% difference between the proportion predicted by HA and that predicted by H0, at a significance level of 0.025 (the significance level calculated by simulation is instead 0.023, thus below the target for the one-tailed test).

There is no inflation of the sample size determined by possible dropouts, as every such subject will automatically be considered a failure.

Incidentally, it is also pointed out that by the time the 19th success is reached, the null hypothesis can already be rejected, as 19 successes out of 49 would represent a proportion of 38.776%, which has an exact 95% binomial confidence interval ranging from 25.197% to 53.761%, so that the maximum proportion of 25% predicted by H0 would be below the lower margin of the confidence interval.

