5.2.2 Primary Endpoint

The primary endpoint will be assessed with one-tailed exact binomial tests, as described in section.

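### Could the dropout-as-failure rule in section 5.1 overwrite a response already observed at week 10?

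*Combined protocol and SAP*

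**What the plan says.** Section 5.1 sets up a one-sample test of a 25% success rate under H0 against 50% under HA. It states that "an exact one-tailed binomial test applied to a sample of 49 subjects achieves a power of 95.7"%, at a one-tailed target of 0.025 with 0.023 attained. It then says: "There is no inflation of the sample size determined by possible dropouts, as every such subject will automatically be considered a failure". It adds that H0 can be rejected as soon as 19 successes have accrued, because the exact 95% interval for 19/49 starts at 25.197%.

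Section 4.14.1 fixes the time: "The primary endpoint will be assessed at 10 weeks and will include" the change in NRS from T0. It calls the result clinically significant if "at least 50% of the treated subjects show a reduction of at least 3 points on the NRS scale".

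Follow-up goes on after that. The Synopsis says "The duration of the study for each subject will be in weeks 24", and section 4.10.2 places the last visit thus: "At 24 weeks from day 0 at the end of the Clinical Investigation". Section 4.16 opens with "Subjects may leave the Clinical study for the following reasons" and lists three reasons, none tied to a visit. Section 5.2.2 adds no dropout rule: "The primary endpoint will be assessed with one-tailed exact binomial tests, as described in section", where the section number is missing.

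**The concern.** Taken word by word, the failure rule has no end date. A subject who leaves between weeks 10 and 24 is a dropout in the ordinary sense, and the rule speaks of all dropouts and of automatic failure. A subject with an observed fall of 3 points or more at week 10 who left at week 18 would then count against the treatment. That would discard a measured primary outcome and bias the success rate downward. Two analysts could code the same subject differently, and each could cite the plan.

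A second, smaller question is attached. Counting dropouts as failures keeps all 49 in the denominator, but it preserves the stated power only if the 50% under HA already includes those failures. Section 5.1 does not say so in as many words.

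At stake would be the primary result near two edges: the test's cut-off at 19 successes, and the 50% clinical criterion, which needs 25 of 49.

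**Working it through.** **Inputs.** From section 5.1: n = 49, H0 25%, HA 50%, one-tailed target 0.025, cut-off 19. From section 4.14.1: endpoint at week 10, criterion of at least 50%. The documents give no dropout rate, so every loss rate below is an assumption.

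**1. The plan's own figures.** With P(X ≥ c | p) = Σ C(49,x) pˣ(1−p)⁴⁹⁻ˣ summed over x = c to 49:
- P(X ≥ 19 | 0.25) = 0.0231 and P(X ≥ 18 | 0.25) = 0.0456, so 19 is the smallest cut-off that meets 0.025.
- P(X ≥ 19 | 0.50) = 0.9573.
- The exact 95% interval for 19/49 is 25.197% to 53.761%.

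All agree with section 5.1.

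**2. What the failure rule refers to.** Three features of the text point the same way.
- The sentence gives the reason for not inflating the sample. Inflation replaces subjects who supply no primary outcome. Someone measured at week 10 who leaves at week 18 costs the primary analysis nothing.
- Section 5.1 defines a success by the 3-point reduction, and section 4.14.1 sets the time at week 10. An observed week-10 responder meets that definition.
- The remark about the 19th success treats a success as final once reached. It does not fit a rule that could revoke successes until week 24.

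**3. Size if the rule were nevertheless applied literally.** Let a share f of week-10 responders leave in weeks 10 to 24. The counted success rate is then 0.50(1−f), or 0.25(1−f) under H0. The expected number of responders is 49 × 0.5 = 24.5, so the expected number recoded is 24.5f.

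| f (assumed) | Responders recoded | Counted rate | Power, P(X ≥ 19) | P(X ≥ 25) | Type I error |
|---|---|---|---|---|---|
| 0 | 0 | 50.0% | 95.7% | 50.0% | 0.023 |
| 2% | 0.5 | 49.0% | 94.3% | 44.4% | 0.019 |
| 5% | 1.2 | 47.5% | 91.5% | 36.2% | 0.014 |
| 10% | 2.5 | 45.0% | 84.6% | 24.0% | 0.008 |

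The 25-or-more column starts at 50% because the true rate is set exactly at the criterion.

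**4. The edges.** One recoded responder moves 19/49 (p = 0.0231) to 18/49 (p = 0.0456). At a true 50%, exactly 19 successes has probability 0.9573 − P(X ≥ 20) = 0.9573 − 0.9238 = 0.0335. One recoded responder also moves 25/49 = 51.0% to 24/49 = 49.0%; exactly 25 has probability 11.2%, and the test still rejects at 24 (p = 0.0002). Starting from 25 successes, 25 − 18 = 7 reversals are needed to lose rejection.

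**5. Whether the 50% is net of dropouts.** If a share d is lost before week 10 and the 50% is net, assessed subjects must respond at 0.50/(1−d): 52.6, 55.6, 58.8 and 62.5% for d = 5, 10, 15 and 20%. Power stays at 95.7%. If the 50% were instead the rate with complete week-10 data, and leaving were independent of response, power would be P(X ≥ 19 | 0.50(1−d)) = 91.5, 84.6, 74.8 and 62.2%. Section 4.14.1 states the 50% as a share of treated subjects, the denominator is all 49, and dropouts are failures within it. Together these define a net rate, which is the case in which the plan's power is right.

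**The case for a change.** The strongest case for amending is that the limit is nowhere written, section 5.2.2 points to an unnumbered section, and in a single-arm study the coding of the primary outcome should be settled before data are seen. Section 4.16 even allows a subject to leave at the investigator's discretion. The rule also names only dropouts, so a subject who stays in the study but misses the week-10 visit has no assigned outcome. A sentence or two would settle this at no cost in patients or visits.

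The observation stands: the wording is incomplete. It does not show that the plan would produce a wrong analysis. The purpose of the sentence, the week-10 definition and the 19th-success remark already lead an analyst to keep an observed response. The missed-visit case is detail of the same kind; with a denominator of 49, counting such a subject as a failure is the obvious extension. A rule that anyone with a week-10 score is analysed as observed would go further than clarification: it would also cover a subject who leaves before week 10 but is still measured. Counting early leavers as failures is a legitimate composite choice, and there is no statistical reason to reverse it.

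**Conclusion.** No change is needed. Section 5.1 leaves out a time limit that its own context supplies: the rule is for subjects lost before the week-10 assessment, and an observed week-10 outcome stands. This is a gap that analysts fill sensibly.

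If it were filled the other way, the error would be conservative. Power would be between 94.3% and 84.6% for an assumed 2 to 10% of responders leaving late, and type I error would fall below 0.023, so a false positive would not become more likely. A changed conclusion needs a count right at 19 or 25, or several late-leaving responders.

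The 95.7% power, the 0.023 and the 19/49 cut-off are correct for a 50% success rate over all 49 treated subjects. No power shortfall is shown on that reading, which the wording supports. The lower powers in step 5 of the working belong to the less supported reading and to loss rates that the documents do not give.

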5.2 Statistical Analysis Plan

5.2.1 Descriptive statistics

All variables will be subjected to the appropriate descriptive analyses after validation of the input data. Continuous variables: mean ± standard deviation or median and range, depending on the distribution; categorical variables: absolute and relative frequency tables.

5.2.2 Primary Endpoint

The primary endpoint will be assessed with one-tailed exact binomial tests, as described in section.

5.2.3 Secondary Endpoints

Foreword: for all continuous variables, an attempt will always be made to use the parametric test; in the case of non-Gaussian distribution (possibly assessed after Shapiro-Wilk tests) or non-

homogeneous variance, an attempt will however be made to modify the variable with the use of a nonlinear transform (logarithm, ladder, etc.) before using the non-parametric equivalents.

The tests provided for the secondary endpoints are:

- NRS score assessment at time weeks 6 and weeks 24 compared to time day0: anova to repeated measures within subject or Friedman test.
- Evaluation of mHHS score time weeks 6, weeks 10, and weeks 24 compared to time day 0. Test Anova to repeated measures within subject or Friedman test.
- Clinical evaluation of stenia in abduction at time weeks 6, weeks 10, and weeks 24 compared to time day 0: Anova at repeated measurements within subject or Friedman's test
- Evidence of resolution or decrease in inflammatory and degenerative signs of the peritrochanteric region of the GTPS-affected hip, on MRI investigation at weeks 24 compared to day 0: Student's t-test for paired data or Wilcoxon test.
- Assessment of analgesic drug unit consumption based on clinical diary at day 0, week 1, weeks 2, weeks weeks 10, and weeks 24 compared to time day 0: repeated measures Anova or Friedman test.
- Assessment of the fraction of subjects leaving the clinical investigational early in relation to Adverse Events (AE/SAE/SUSAR): measurement of absolute and relative frequency and 95% confidence interval.

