4.14.2 Secondary End Points

- Evaluation of the NRS score at time weeks 6 and weeks 24 compared to time day 0.
- Evaluation of mHHS score at time weeks 6, weeks 10, and weeks 24 compared to time day 0.

_

- Clinical evaluation of abduction stenia at time weeks 6, weeks 10, and weeks 24 compared to time day 0.
 - [the stenia will be assessed, with the subject standing on the healthy limb, through measurements of the abduction force of the GTPS-affected hip, using a dynamometer]
- Evidence of resolution or decrease in inflammatory and degenerative signs of the peritrochanteric region of the GTPS-affected hip on MRI investigation at weeks 24 compared to day 0.
- Assessment of analgesic drug unit consumption based on clinical diary at day 0, week 1, week 2, weeks 6, weeks 10 and weeks 24.
 - [Celecoxib 200mg cpr 1 tablet/day will be used as a pain killer, in case of onset/recurrence of pain; if the subject is hypertensive or intolerant Paracetamol 1000mg cpr 2 tablets/day].
- Evaluation of the fraction of subjects who drop out of the Clinical Investigation Plan early in relation to Adverse Events (AE/SAE/SUSAR).

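### Section 5.2.3 tests NRS, mHHS and abduction strength only with omnibus methods, so the change from day 0 that each endpoint asks about is neither estimated nor given an interval, and missing scores have no rule

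*Combined protocol and SAP*

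**What the plan says.** Section 4.14.2 words these endpoints visit by visit. For pain it is "Evaluation of the NRS score at time weeks 6 and weeks 24 compared to time day 0". For mHHS and abduction strength the visits are weeks 6, 10 and 24, again against day 0.

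Section 5.2.3 then names the analysis. For pain it is "NRS score assessment at time weeks 6 and weeks 24 compared to time day0: anova to repeated measures within subject or Friedman test". The mHHS and strength bullets name the same pair of methods. None of the three mentions a follow-up comparison, a change estimate or a confidence interval. The only interval in that section is for the fraction of subjects leaving early in relation to adverse events.

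The foreword to section 5.2.3 sets an order of methods: "an attempt will always be made to use the parametric test", then a nonlinear transform (logarithm, ladder or similar) if the distribution is not Gaussian or variances are unequal, then the non-parametric equivalent. Shapiro-Wilk is named only as a possible check.

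On summaries, section 5.2.1 says "All variables will be subjected to the appropriate descriptive analyses" and specifies mean with SD, or median with range. Section 4.16 allows subjects to leave early. The only rule for dropouts is in section 5.1: "every such subject will automatically be considered a failure".

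**The concern.** Repeated-measures ANOVA and Friedman ask whether the visits differ among themselves at all. The endpoints ask how far the score at a given visit has moved from day 0. The first answer does not supply the second. A clear early improvement that had vanished by week 24 would still give a significant omnibus result, and a reader could take it as support for a lasting effect.

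Two further gaps add to this. A result on a transformed scale is not in NRS points, the unit in which section 4.14.1 defines success. And counting a dropout as a failure works for a yes/no endpoint but cannot supply a score, so how many subjects stand behind each secondary result depends on how the test happens to be run.

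**Working it through.** **The plan's own figures.** The documents state no number for the secondary analyses. The primary figures in section 5.1 reproduce. With rejection at 19 or more successes of 49, P(X ≥ 19 | 49, 0.25) = 0.0231 (stated 0.023) and P(X ≥ 19 | 49, 0.50) = 0.957 (stated 95.7%). The exact 95% interval for 19/49 is 25.197% to 53.761%, as stated. Nothing below touches these.

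**Does the omnibus test answer the week-24 question?** Simulation with n = 49, three visits and within-subject correlation 0.5 (assumed), 3,000 runs, tests at 5%:

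| True change from day 0 | RM-ANOVA rejects | Friedman rejects |
|---|---|---|
| 1 SD at week 6, none at week 24 | 100% | 100% |
| None at any visit | 4.9% | 5.3% |

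Both tests hold their level, yet both always reject when week 24 equals day 0. The same happened with four visits and a change at weeks 6 and 10 only.

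**Do the descriptive summaries fill the gap?** A difference in means can be read off two visit summaries, but its uncertainty cannot. If both visits have SD s, the SD of change is s·√(2(1 − r)), where r is the correlation between visits. At r = 0.5 this is 1.00s; at r = 0.7 it is √0.6·s = 0.77s. No report of r, or of the SD of change, is planned.

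**Complete cases, if complete sets of visits are required.** The documents give no dropout rate, so the missing fraction p is assumed: 10%, range 5–20%.

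| Pattern | Formula | p = 5% | p = 10% | p = 20% |
|---|---|---|---|---|
| NRS, 2 follow-up visits missed independently | 49(1 − p)² | 44.2 | 39.7 | 31.4 |
| mHHS or strength, 3 visits missed independently | 49(1 − p)³ | 42.0 | 35.7 | 25.1 |
| Withdrawal spread evenly, total p by week 24 | 49(1 − p) | 46.6 | 44.1 | 39.2 |

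In the last pattern, 49(1 − p·6/24) = 48.4, 47.8 and 46.6 subjects are seen at week 6. A complete-case test would therefore set aside about 1.8, 3.7 and 7.4 observed week-6 scores.

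**Size of the interval that is not planned.** Half-width = t(0.975, n − 1)·SD/√n. The SD of NRS change is assumed to be 1.5 to 2.5 points, because the documents give none.

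| n | t/√n | SD 1.5 | SD 2.5 |
|---|---|---|---|
| 49 (all observed) | 0.287 | ±0.43 | ±0.72 |
| 44 (even withdrawal, 10%) | 0.304 | ±0.46 | ±0.76 |
| 40 (independent, 10%) | 0.320 | ±0.48 | ±0.80 |

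At a 10% missing rate, complete-case analysis costs the NRS interval about 0.03 to 0.08 points of half-width. That is modest; the larger defect is that no interval is planned.

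**Multiplicity of visit-wise reporting.** The listed contrasts number 2 (NRS) + 3 (mHHS) + 3 (strength) = 8. Unadjusted at 5% and treated as independent, 1 − 0.95⁸ = 0.34.

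**The case against.** The plan does fix the reference time and the comparison visits, so the intended comparison is clear, and follow-up contrasts could be taken as implied. Descriptive summaries will show the pattern. Repeated-measures ANOVA can be fitted as subject plus visit effects. That form accepts incomplete subjects: with 49 subjects, three visits and five missing at week 24, all 49 × 3 − 5 = 142 observations enter, and the day-0 contrasts are its coefficients. These are also secondary endpoints in a one-sample pilot, and none decides success.

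Much of this stands. What is missing is how the comparison is estimated and reported, not which comparison is meant. The need for complete sets of visits is firm for Friedman but depends on implementation for ANOVA. It remains true that no estimate, interval or missing-score rule is written down. Estimates with intervals are also what a pilot is most useful for, and section 5.10 aims at reliable conclusions on clinical efficacy.

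Three stronger readings are tempting but unsupported:

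- A reader might infer that subjects will certainly be lost from the ANOVA. The text does not specify a complete-case version, and section 4.16 lists reasons for leaving without saying when or how often this will happen.
- A reader might infer that the normality check will usually force a transform or a rank test. The order of methods is set in advance, and the documents give no means, SDs or correlations from which a switching rate could be worked out.
- A reader might infer that week-10 NRS has been wrongly left out of the secondary analysis. Section 4.14.2 does not list it; week 10 is the primary time point.

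**Conclusion.** The point holds. For NRS, mHHS and abduction strength, the named tests do not deliver the visit-by-visit comparison with day 0 that section 4.14.2 defines. No change estimate or interval is planned, a transformed result would lose the score units, and no rule covers missing scores.

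The shortfall in interpretation follows from the text and from what an omnibus test is. The numerical sizes rest on assumptions: 5–20% missing, an SD of NRS change of 1.5 to 2.5 points, and complete-case handling. This is an improvement that should be made. It is not a flaw in the primary analysis: N = 49, the threshold of 19 successes, the attained level of 0.0231 and the power of 0.957 all stand.

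**What to change.** In section 5.2.3, for each of the three scores, make the main secondary analysis the change from day 0 at each listed visit, in original units, with a 95% CI and the number observed. Either of two methods would do:

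- a mixed model for repeated measures on all observed data, with visit as a categorical factor, the covariance structure named and the missing-at-random assumption stated; or
- more simply, paired differences on all available pairs at each visit.

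Use a paired Wilcoxon test per visit as a sensitivity analysis, in place of the data-driven transform step for these scores. Label the eight listed contrasts supportive and unadjusted. Week-10 NRS as a score may be added as a ninth (1 − 0.95⁹ = 0.37). The analgesic-consumption bullet has the same omnibus test and day-0 wording, so apply the same visit-wise reporting there or say why not.

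The cost is SAP wording and minor programming, with no new data or subjects. The downsides are reliance on missing-at-random (paired differences need the available pairs to be representative) and about a 34% chance of at least one false positive among eight contrasts if they are independent. With no control group, the change describes improvement and not a device effect, and the report should say so.
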